### **Full Analysis Set (FAS)**

The FAS will serve as a supportive analysis population for Immunogenicity. The FAS population consists of all randomized participants who received at least 1 vaccination and have at least one post-randomization observation for the analysis endpoint.

### **9.5.2 Safety Analysis Populations**

The All Participants as Treated (APaT) population will be used for the analysis of safety in this study. The APaT population consists of all randomized participants who received at least one vaccination and defined according to the regimen of clinical material actually received (ie, received only vaccine, or received only placebo). Participants who received a mixture of vaccine and placebo are deemed ineligible for inclusion in the APaT population. Safety data of participants ineligible for inclusion in the APaT population will be summarized in listings.

## **9.6 Statistical Methods**

### **9.6.1 Statistical Methods for Immunogenicity Analyses**

CMV-specific NAb GMT at 1 month PD3 will be analyzed for seronegative participants using an ANOVA model. The NAb titers will be log-transformed prior to analysis. The model will include term for intervention. The treatment difference and corresponding 95% confidence interval (CI) will be estimated at 1 month PD3 on the log-transformed data. Estimates of treatment difference and corresponding 95% CI will then be back-transformed to get the GMT ratio and the 95% CI for GMT ratio. Methods related to exploratory endpoint will be described in sSAP.

Table 3 summarizes the analysis plans relating to the immunogenicity endpoints.

Table 3 Analysis Strategy for Key Efficacy Variables

Endpoint/Variable (1 month PD3)	Primary vs. Supportive Approach †	Statistical Method	Analysis Population	Missing Data Approach
Secondary				
CMV-specific NAb GMT at 1 month PD3	P	ANOVA	PPI (seronegative participants)	observed data
CMV-specific NAb GMT at 1 month PD3	S	ANOVA	FAS (seronegative participants)	observed data

† P=Primary approach, S=Supportive approach.  
ANOVA: analysis of variance, PPI:Per Protocol Immunogenicity, FAS: Full Analysis Set

#### Handling of Missing Data

All analyses will be conducted based on the observed data only.

#### **9.6.2 Statistical Methods for Safety Analyses**

Safety and tolerability will be assessed by clinical review of all relevant parameters including AEs and vital signs. All participants who are vaccinated and eligible for inclusion in the APaT population as defined in Section 9.5.2 will be included in the safety analyses and summaries. Incidence of AEs will be summarized as frequencies and percentages by vaccination group.

To provide an overall assessment, safety measures such as the incidence of the following events occurring throughout the study will be summarized for each serostatus, respectively:

- 1) any AE,
- 2) any injection-site AE,
- 3) any systemic AE,
- 4) any SAE,
- 5) any vaccine-related SAE,
- 6) any discontinuation due to an AE within 14 days of receipt of any study vaccination

AEs will be summarized by vaccination visit and across all vaccination visits. Specific AEs for which summaries will be provided are identified in [Table 4](#).

- The number and percent of the participants with positive viral shedding in urine and saliva up to 1 month postdose 3 (defined by viral load in saliva/urine  $\geq$  assay defined threshold cutoff value) will be also summarized for generic CMV and for vaccine-type virus separately, by vaccination group by CMV serostatus.
- The number and percent of the participants with positive viral detection in plasma up to 14 days postdose 1 (defined by viral load in plasma  $\geq$  assay defined threshold cutoff value) will be also summarized for generic CMV and for vaccine-type virus separately, by vaccination group by CMV serostatus.
- The number and percent of the participants with positive viral leakage in injection-site swab and adhesive tape swab up to 30 minutes postdose 1 (defined by viral load in injection-site swab/adhesive tape swab  $\geq$  assay defined threshold cutoff value) will be also summarized for generic CMV by vaccination group by CMV serostatus.
- The oral temperatures recorded on the VRC will also be summarized.

Table 4 Safety Analyses of Adverse Events Endpoints

Adverse Events endpoints	Time Window		
	Day1 to Day 5 †	Day 1 to Day 14 †	Any Time during Study
-Solicited Injection site AEs of pain/tenderness, erythema/redness, and swelling	●		
-Unsolicited injection site AEs		●	
-Solicited systemic AEs of fatigue, myalgia, headache and arthralgia		●	
-Unsolicited systemic AEs		●	
-Serious AEs		●	
-VR SAEs		●	
- Discontinuation due to an AE		●	
-Elevated temperature §		●	
-Death			●
-Any AE		●	
-Saliva/Urine viral Shedding*			●
-Viral detection from plasma*			●
-Viral leakage from swab sampling of injection-site/adhesive tape*			●

Summaries will be provided by vaccination group separately for the participants in each serostatus.

† The day of vaccination is counted as Day1. Day 1 to Day 5 refers to the day of vaccination plus 4 days immediately post-vaccination.  
Day 1 to Day 14 refers to the day of vaccination plus 13 days immediately post-vaccination.

\* The viral shedding, viral detection from plasma, and viral leakage data will be summarized as percentage of positivity by Visit; the duration for collecting viral shedding is shown in SoA.

§ Defined as  $\geq 38.0^{\circ}\text{C}$  oral or equivalent.

AE=Adverse Events, SAE=Serious Adverse Events, VR=Vaccine-Related.

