### 2.2.2.2 Clinical Studies

#### Phase 1 Clinical Study

The first-in-human study was a Phase 1 dose ranging study to assess the safety and immunogenicity of various antigen dose levels, formulations, and routes of administration in healthy volunteers 18 years of age and older (V160-001) in United States. In study V160-001, the safety and tolerability as well as the immunogenicity of V160 was evaluated in both CMV seronegative and seropositive participants and is briefly summarized below. Refer to the IB for more detailed information.

Participants in study V160-001 received a 3-dose vaccination regimen (0-1-6 month schedule) at various doses (10-250 units) administered intramuscularly or intradermally, with and without aluminum phosphate adjuvant. A saline placebo was used as the control.

In initially CMV seronegative participants, all vaccination groups receiving V160 with and without aluminum phosphate adjuvant exhibited statistically significant higher CMV-specific NAb titers compared with the placebo group. The NAb geometric mean titer (GMT) at Month 7 was highest in recipients of V160 100 unit dose + aluminum phosphate adjuvant.

Robust cell mediated immune responses were also noted among CMV seronegative participants but no differences across dose groups of V160 were observed. Overall, cell mediated immune responses at all doses, and NAb responses at some doses (including 100U+ aluminum phosphate adjuvant) in CMV seronegative participants approximated those observed in naturally infected CMV seropositive participants.

All tested V160 formulations were safe and generally well-tolerated. No SAEs and no events of clinical interest (ECIs) (overdoses, pre-defined elevated hepatic enzyme, and autoimmune conditions) were reported. Overall, adjuvant-containing formulations were more reactogenic than unadjuvanted irrespective of dose. Across the different vaccination groups, the majority of AEs were the solicited injection site AEs (pain/tenderness, erythema/redness, and swelling) and the solicited systemic AEs (headache, fatigue, muscle pain, and joint pain); all of these events were transient and most were mild to moderate in intensity. No vaccine strain CMV was detected by polymerase chain reaction (PCR) in the saliva or urine of vaccine recipients.

Refer to the IB for further details regarding viral replication, virological characteristics of the vaccine virus, as well as detailed background information on animal studies.

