## 3 HYPOTHESIS, OBJECTIVES, AND ENDPOINTS

There are no hypotheses for the study.

The following objectives will be evaluated in healthy Japanese male participants 20 years to 64 years of age inclusive.

Objectives	Endpoints
Primary	
To assess the safety and tolerability of a 3-dose regimen of V160 administered intramuscular (IM) by cytomegalovirus (CMV) serostatus.	

Solicited injection site adverse events (AEs) within Days 1 through 5 after each vaccination visit, and solicited systemic AEs, and vaccine-related serious adverse events (SAEs) within Days 1 through 14 after each vaccination visit

Secondary	
To evaluate CMV-specific neutralizing antibody (NAb) geometric mean titers (GMTs) at 1 month postdose (PD)3 in initially CMV-seronegative participants vaccinated with a 3-dose regimen of V160 administered IM.	

CMV-specific NAb titers

To evaluate viral detection, viral shedding, and viral leakage of V160 by the number and proportion of the participants with positive viral detection in plasma up to 14 days PD1, in urine and saliva up to 1 month PD3, and in injection-site swab and adhesive tape swab up to 30 minutes PD1 by CMV serostatus.	

Viral detection of V160 in plasma, urine and saliva, and injection-site swab and adhesive tape swab

Exploratory	
To evaluate seroconversion rate based on the NAb titers at 1 month PD3 in initially CMV-seronegative participants vaccinated with a 3-dose regimen of V160 administered IM.	

Seropositivity based on the NAb titers

To evaluate NAb GMT and geometric mean of CMV-specific NAb fold-rise (GMFR) at 1 month PD3 relative to Day 1 in initially CMV-seropositive participants vaccinated with a 3-dose regimen of V160 administered IM.	

CMV-specific NAb titers

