#### 4.2.1.2 Safety Endpoints

The safety endpoints evaluated in this study were selected based on the product's safety profile demonstrated in study V160-001.

In this study, as in study V160-001, solicited injection site AEs will be collected Days 1 to 5 following each dose of V160/placebo, and oral temperatures and pre-specified solicited systemic AEs including tiredness (fatigue), muscle pain (myalgia), headache, and joint pain (arthralgia) will be collected Days 1 to 14 following each dose of V160/placebo. SAEs will be collected for the duration of the participant's study participation (up to Month 7/Visit 8). The vaccine is conditionally replication defective and the vaccine virus will not replicate in the human body because Shield-1 is not present, regardless, specific safety measurements are being collected as outlined in Section 8.4.

The time points chosen for safety assessment are based on peak occurrence of AEs generally observed following vaccination in clinical studies with multi-dose vaccines. The investigator (or medically-qualified designee) will assess the vaccine relatedness of all serious and non-serious AEs, the intensity of all serious and non-serious AEs. During the Vaccination Report Card (VRC)-specified safety follow-up period (Day 1 through Day 14), clinical AEs will be recorded on a VRC by the participant on the day of occurrence. The investigator will use the information provided by the participant both on the VRC, and verbally at the time of VRC review.

Details on AEs, including definitions and reporting requirements, can be found in Appendix 3.

In addition, samples of saliva, urine, injection-site swab and adhesive tape swab will be collected at pre-specified times according to the SoA to evaluate the possible shedding, and leakage from the injection-site using a sensitive PCR assay. Furthermore, samples of blood (plasma) will be collected at pre-specified times up to Day 14 (SoA) as well to evaluate the possible biodistribution of vaccine virus in plasma using PCR assay.

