### 8.3.3 Safety Assessments Using the VRC

All participants will be observed for 30 minutes after each vaccination for any immediate reactions. If any immediate AEs are observed during this period, the time at which the event occurred within this timeframe, as well as the event itself, any concomitant medications that were administered, and resolution of the event, must be recorded on the appropriate eCRF.

Participants will use the VRC (Section 8.1.11) to document the following information:

- Oral temperatures measured from Day 1 (day of vaccination) through Day 14 postdose; any temperature  $\geq 38.0^{\circ}\text{C}$  oral or equivalent, will be considered an AE of fever.
- Solicited injection site AEs (pain/tenderness, erythema/redness, and swelling) from Day 1 through Day 5 postdose;
- Solicited systemic AEs (headache, tiredness, muscle pain, and joint pain) from Day 1 through Day 14 postdose;
- Any other injection-site or systemic AEs from Day 1 through Day 14 postdose; and
- Concomitant medications from Day 1 to Day 14 postdose.

In order to ensure that the VRC is being filled out without delay, telephone contacts to remind the subject will be conducted after 14 days from the second and the third vaccination, respectively.

The investigator or delegate will review the data captured on the VRC with the participant at the subsequent visit after each vaccination (refer to the SoA).

For AEs reported on the VRC, the investigator will use the information provided by the participant both on the VRC, and verbally at the time of VRC review, to apply the appropriate intensity grade as described in Appendix 3.

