### **Assessment of intensity**

- An event is defined as “serious” when it meets at least 1 of the predefined outcomes as described in the definition of an SAE, not when it is rated as severe.
- The investigator will make an assessment of intensity for each AE and SAE (and other reportable safety event) reported during the study and assign it to 1 of the following categories:
  - Mild: An event that is easily tolerated by the participant, causing minimal discomfort and not interfering with everyday activities (for pediatric studies, awareness of symptoms, but easily tolerated).
  - Moderate: An event that causes sufficient discomfort to interfere with normal everyday activities (for pediatric studies definitely acting like something is wrong).
  - Severe: An event that prevents normal everyday activities. An AE that is assessed as severe should not be confused with an SAE. Severe is a category utilized for rating the intensity of an event; and both AE and SAE can be assessed as severe (for pediatric studies, extremely distressed or unable to do usual activities).
- Injection site erythema/redness or swelling from the day of vaccination through Day 5 postvaccination will be evaluated by maximum size.

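### Tolerability is part of the primary objective, but the planned adverse event summaries are incidence only: collected intensity and redness/swelling size go unreported, and relatedness is summarised only for SAEs

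*Combined protocol and SAP*

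**What the plan says.** Section 3 states the primary objective: "To assess the safety and tolerability of a 3-dose regimen of V160 administered intramuscular (IM) by cytomegalovirus (CMV) serostatus". The primary endpoints are the occurrence of solicited injection-site AEs (Days 1 to 5), and of solicited systemic AEs and vaccine-related SAEs (Days 1 to 14).

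More than occurrence is collected. Under Section 4.2.1.2 the investigator "will assess the vaccine relatedness of all serious and non-serious AEs, the intensity of all serious and non-serious AEs". For events on the Vaccination Report Card, Section 8.3.3 has the investigator use the card and the participant's verbal account "to apply the appropriate intensity grade as described in Appendix 3". Appendix 3 supplies a three-level scale (mild, moderate, severe) based on interference with everyday activities, applied to all events: "The investigator will make an assessment of intensity for each AE and SAE". It then adds: "Injection site erythema/redness or swelling from the day of vaccination through Day 5 postvaccination will be evaluated by maximum size".

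On analysis, Section 9.6.2 says: "Incidence of AEs will be summarized as frequencies and percentages by vaccination group". It lists six overall measures, to be given for each serostatus, and refers to Table 4 for the specific AE rows, with summaries by vaccination visit and across visits. Sections 9.1 and 9.4.2 likewise speak only of incidence or occurrence.

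**The concern.** The trial has no hypotheses, no interim analysis and no data monitoring committee, so the descriptive safety tables are the primary analysis. Whether a vaccine is tolerable depends on how bad the reactions are as well as how many participants have one. The protocol's own account of the first-in-human study shows this: among its grounds for calling the formulations generally well tolerated, it reports of the solicited events that "all of these events were transient and most were mild to moderate in intensity". It also reports that adjuvanted formulations were more reactogenic than unadjuvanted ones, and here an adjuvanted vaccine is compared with saline. Some excess of local reactions is foreseeable, and readers will then ask about their severity. Tables built exactly to Section 9.6.2 and Table 4 would not answer that, although the data needed would be in the database.

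**Working it through.** **Step 1. What is collected against what is summarised.**

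| Attribute | Collected for | Source | Planned summary |
|---|---|---|---|
| Occurrence | every AE in the reporting window | 8.3.3, 8.4.1 | yes: 9.6.2, Table 4 |
| Intensity | every AE and SAE | 4.2.1.2, 8.3.3, Appendix 3 | none |
| Maximum size | redness and swelling, through Day 5 | Appendix 3 | none |
| Relatedness | every AE and SAE | 4.2.1.2, Appendix 3 | vaccine-related SAEs only |

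**Step 2. Could severity show in another row?** The severity-linked rows in 9.6.2 and Table 4 are SAEs, vaccine-related SAEs, death, discontinuation due to an AE, and temperature of 38.0 °C or above. Appendix 3 itself distinguishes severe from serious. A severe but non-serious episode of pain, headache or myalgia that does not end vaccination is counted in its own solicited row and in the any-AE type rows, exactly as a mild episode would be.

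**Step 3. Is it deferred elsewhere?** Section 9 gives the supplemental SAP the analysis changes made after protocol finalisation and before unblinding. Section 9.6.1 gives it the methods for the exploratory endpoint, within the immunogenicity methods. Neither assigns it AE grading. The only safety listings named (9.5.2) are for participants ineligible for the as-treated population.

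**Step 4. Illustration.** The plan gives no figure on intensity to reproduce. Section 9.9 randomises 9 per serostatus at 2:1, so V160 n = 9 × 2/3 = 6. The counts below are assumed, and the intervals are exact 95% limits added here to show resolution.

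- Planned row, all six with pain: 6/6 = 100%, lower limit 0.025^(1/6) = 54.1%. The entry is the same whether all six events are mild or all six are severe.
- A severe-intensity row if all are mild: 0/6 = 0%, upper limit 1 − 0.025^(1/6) = 45.9%.
- A severe-intensity row if all are severe: 6/6 = 100%, interval 54.1% to 100%.
- A smaller contrast, one severe of six: lower limit 1 − 0.975^(1/6) = 0.4%; the upper limit solves (1 − p)^6 + 6p(1 − p)^5 = 0.025, giving about 64%. The interval 0.4% to 64% overlaps heavily with 0% to 45.9%.

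The extreme contrast separates and the small one does not. The added rows would describe severity; they would not estimate it precisely.

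**Side note.** The one numerical safety statement, in Section 9.9 (no events in 6, upper bound 46% at 90% confidence), does not reproduce as labelled: 1 − 0.10^(1/6) = 31.9% one-sided and 1 − 0.05^(1/6) = 39.3% two-sided, while 46% matches the two-sided 95% limit. That is a separate matter and does not affect this point.

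**The case against.** The strongest reply is that the analysis matches the endpoints. The primary endpoints are occurrences and the plan summarises occurrences; no test, estimate or decision rule depends on intensity. Section 9.6.2 also opens with a general clinical review of the relevant safety parameters and introduces its list of measures as examples, so intensity may well be looked at. Report-card temperatures are summarised too. All of this is true, and it limits the point to missing descriptive output. It does not remove the point: the general wording commits to no table, whereas Table 4 is an explicit list, and intensity and size are not on it.

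A reader might infer more than the documents support in four ways.

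- *That redness and swelling have no usable severity result.* Appendix 3 requires an intensity grade for each AE, these two included, and says in addition that they "will be evaluated by maximum size". They carry two measures. The appendix does not link them, but that is not a contradiction, and nothing in the documents favours size over the grade.
- *That local-reaction incidence will sit near 100%, making incidence uninformative.* The first-in-human summary gives no incidence rates. It says solicited events were the majority of AEs, which is a share of events and not a proportion of participants.
- *That the non-overlapping 0/6 and 6/6 intervals show what a severity row would resolve.* That is the most extreme contrast possible; 0/6 against 1/6 does not separate.
- *That relatedness is ignored altogether.* It is used for SAEs; the gap is non-serious AEs, including the solicited ones.

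The first-in-human summary also noted that events were transient. This point makes no claim about duration.

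**Conclusion.** The point holds as a reporting gap in the primary safety analysis. Intensity for all AEs, maximum size for redness and swelling, and relatedness for non-serious AEs are required by the protocol but enter no prespecified summary. In the solicited-AE rows, mild and severe non-serious reactions are indistinguishable. No planned figure is biased or miscalculated, and participants and data collection are unaffected.

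The conclusion rests on Sections 9.1, 9.4.2, 9.6.2 and Table 4 being the full prespecified safety output, and on the supplemental SAP not already covering grading; the documents do not assign that to it. The 6/6 counts are illustrative, and the conclusion does not depend on them or on any assumed reaction rate. The change is worth making because it is nearly free and bears directly on the tolerability half of the primary objective. It would not give precise severity rates at this sample size.

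**What to change.** Before unblinding, add the following to Section 9.6.2 and Table 4, or to the supplemental SAP, using the breakdown already planned (vaccination group, serostatus, vaccination visit and across visits):

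- each solicited AE by the participant's maximum intensity (mild, moderate, severe);
- redness and swelling by recorded maximum size, as individual values or as bands fixed before unblinding, shown alongside the intensity grade and not in place of it;
- rows for any vaccine-related AE and any severe AE.

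State that these rows are descriptive and that, with 6 V160 recipients per stratum, they will resolve only large differences.

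The cost is SAP wording and a few table rows. The protocol already requires the grades, the relatedness judgements and the size evaluation, so no new participants or assessments are needed. The report card form is not among the documents, so the size display should follow whatever measure it records.

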## **7     DISCONTINUATION OF STUDY INTERVENTION AND PARTICIPANT WITHDRAWAL**

### **7.1     Discontinuation of Study Intervention**

Discontinuation of study intervention does not represent withdrawal from the study.

As certain data on clinical events beyond study intervention discontinuation may be important to the study, they must be collected through the participant's last scheduled follow-up, even if the participant has discontinued study intervention. Therefore, all participants who discontinue study intervention prior to completion of the vaccination regimen will still continue to participate in the study as specified in Section 1.3.

Participants may discontinue study intervention at any time for any reason or be discontinued from the study intervention at the discretion of the investigator should any untoward effect occur. In addition, a participant may be discontinued from study intervention by the investigator or the Sponsor if study intervention is inappropriate, the study plan is violated, or for administrative and/or other safety reasons. Specific details regarding procedures to be performed at study intervention discontinuation are provided in Section 8.1.9.

A participant must be discontinued from study intervention but continue to be monitored in the study for any of the following reasons:

- The participant or participant's legally acceptable representative requests to discontinue study intervention.
- The participant's intervention assignment has been unblinded by the investigator, Sponsor, or through the emergency unblinding call center.
- The participant has a medical condition or personal circumstance which, in the opinion of the investigator and/or Sponsor, placed the participant at unnecessary risk from continued administration of study intervention.
- The participant had an allergic reaction or an anaphylactic/anaphylactoid reaction that required medical intervention following Dose 1 or Dose 2 administration
- The participant enrolled in another interventional clinical study following Dose 1 or Dose 2 administration.
- The participant has received any prohibited medications or vaccinations since Dose 1 or Dose 2 administration (See Section 5.2.1 for prerequisites for the second and third vaccination visits).

For participants who are discontinued from study intervention but continue to be monitored in the study, see Section 1.3 and Section 8.1.9 for those procedures to be completed at each specified visit.

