#### **8.1.8.1 Timing of Dose Administration**

Dose 1 of study intervention for both V160 and placebo groups will begin on the day of intervention randomization at Visit 2 (Day 1). A second dose of study intervention will be given at Visit 6 (Month 2) and a third dose will be given at Visit 7 (Month 6).

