Non-Serious Adverse Event (NSAE)	Report if: - due to protocol-specified intervention - causes exclusion - participant is receiving placebo run-in or other run-in treatment	Report all from the time of each vaccination through 14 days thereafter.	Not required	Per data entry guidelines
Serious Adverse Event (SAE)	Report if: - due to protocol-specified intervention - causes exclusion - participant is receiving placebo run-in or other run-in treatment	Report all for the duration of an individual's study participation.	Report if: - drug/vaccine related. - any death until participant completion of study (Follow ongoing to outcome)	Within 24 hours of learning of event
Cancer	Report if: - due to intervention - causes exclusion	Report all for the duration of an individual's study participation.	Not required	Within 5 calendar days of learning of event
Overdose	Report if: - receiving placebo run-in or other run-in medication	Report all for the duration of an individual's study participation.	Not required	Within 5 calendar days of learning of event

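### Section 9.6.2 ties discontinuation due to an AE to 14 days after a dose without saying what the 14 days apply to; under either reading some AE-driven discontinuations go uncounted

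*Combined protocol and SAP*

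**What the plan says.** Section 9.6.2 introduces its overall safety list by saying that "the incidence of the following events occurring throughout the study will be summarized for each serostatus, respectively". Item 6 of that list is "any discontinuation due to an AE within 14 days of receipt of any study vaccination". In Table 4 the row for "discontinuation due to an AE" is marked under Day 1 to Day 14 and not under the any-time column, which the table does use for death and for the viral endpoints. The table footnote fixes the window: "Day 1 to Day 14 refers to the day of vaccination plus 13 days immediately post-vaccination".

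For data collection, Table 2 in Section 8.4.1 says of non-serious AEs: "Report all from the time of each vaccination through 14 days thereafter". For SAEs it says: "Report all for the duration of an individual's study participation".

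Section 8.1.2 places an additional review of the deferment, exclusion and discontinuation criteria at Visits 6 and 7. The grounds in Section 7.1 include an allergic or anaphylactic reaction after Dose 1 or Dose 2, and a condition that "placed the participant at unnecessary risk from continued administration of study intervention". Neither carries a time limit. Section 7.1 also lets participants stop at any time, and lets the investigator stop dosing for an untoward effect.

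**The concern.** The primary objective is the safety and tolerability of a 3-dose regimen. Failing to receive the next dose because of an AE is a direct tolerability result, and item 6 with its Table 4 row is where the plan tabulates it.

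The row has three weaknesses. It is limited to 14 days in a list said to cover the whole study. It does not say which date must fall in the 14 days, so two programmers could get different counts from the same data. It also does not say whether discontinuation means stopping vaccination or leaving the study. With 6 V160 recipients per serostatus (Section 9.9), a single case decides whether the row reads 0 or not.

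**Working it through.** The plan states no figure for this point, so there is none to reproduce. The check sets the visit calendar against the 14-day windows.

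**Inputs**
- Dose 1: Day 1. Dose 2 (Visit 6): Day 60, window +14, so Days 60-74. Dose 3 (Visit 7): Day 180, window +14, so Days 180-194 (Schedule of Activities; Table 5).
- Window length: 14 calendar days, counting the day of vaccination as Day 1 (Table 4 footnote).

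**Windows at nominal visits**
- Dose 1: Days 1-14
- Dose 2: Days 60-73
- Dose 3: Days 180-193

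**Gaps between doses**
- Days 15-59: 59 − 15 + 1 = 45 days
- Days 74-179: 179 − 74 + 1 = 106 days

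Table 2 and item 6 could each be read as running one day longer than the Table 4 window. That moves the start of each gap by a day and changes nothing else.

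**Time from the previous dose to the next dosing visit**
- Dose 1 to Visit 6: 60 − 1 = 59 days at the earliest, 74 − 1 = 73 at the latest
- Dose 2 to Visit 7: 180 − 74 = 106 days at the shortest, 194 − 60 = 134 at the longest

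**Reading A: the discontinuation must fall within 14 days.** A participant reacts on, say, Day 3, and Dose 2 is first withheld at Visit 6. The discontinuation is dated at least 59 days after Dose 1 and is not counted.

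The position after Dose 2 is weaker still. There are visits on Days 3, 7 and 14 after Dose 1, but after Dose 2 the schedule has only a telephone reminder about the report card. Section 8.3.3 has the card reviewed at the next visit, which is Visit 7, at least 106 days after Dose 2.

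**Reading B: the AE must start within 14 days.** The Day 3 reaction is now counted, whenever the dose is withheld. An AE that starts on Days 15-59 or 74-179 and stops dosing is not counted. If it is non-serious, Table 2 does not require it to be reported, so it may have no AE record. If it is serious, Table 2 requires the report, but the event still falls outside this row.

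**What else would show the case.** Section 9.6.3 displays the primary reason for discontinuation with no time window. It carries no AE term, intensity or causality. The report could therefore show 0 in the safety table and 1 AE discontinuation in the disposition display.

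**Illustration of size.** One uncounted case among 6 V160 recipients of one serostatus is the difference between 0/6 = 0% and 1/6 = 16.7%. That holds for any event missed in a group of 6; it says how coarse the table is, not how likely a miss is.

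**The case against.** The strongest reply is that Reading B is the more natural one. In item 6 the time limit directly follows the mention of an AE, Table 4 is a table of AE endpoints, and its window matches the AE collection period. On that reading the commonest case one would worry about, an early reaction that leads to a withheld dose, is counted. This largely stands, but the text does not settle it, and Reading B leaves its own gap.

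Second, decisions need not wait for Month 2 or Month 6. Section 7.1 allows discontinuation at any time, and Visits 6 and 7 are an additional review. This stands: a decision taken within 14 days of a dose is counted under both readings.

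Third, the cases are not invisible. Section 9.6.3 shows the reason, Section 9.11 shows how many received each dose, Section 6.4 requires written documentation when the vaccination plan is interrupted, and Table 2 requires SAEs throughout participation. This also stands. What is lost is the entry in the safety row and, for a late non-serious AE, possibly the AE record.

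Fourth, limiting routine non-serious AE reporting to 14 days is a deliberate design choice, tied in Section 4.2.1.2 to when AEs generally peak. That is reasonable for AEs at large. It does not explain why an AE serious enough in its consequences to end dosing should be exempt.

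A reader might go further and infer that most AE-driven discontinuations cannot be counted, pointing out that the first two windows cover 28 of the 179 days from Dose 1 to Dose 3 (28/179 = 15.6%). The documents do not support this. The percentage is calendar coverage; it would measure what is missed only if such discontinuations were spread evenly over time, and the documents give no timing for AEs or for discontinuations. A reader might also infer that the window after Dose 3 is necessarily empty. That is true of stopping vaccination, but item 6 says any discontinuation, and a participant can still leave the study between Dose 3 and Month 7.

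**Conclusion.** The point holds as a gap and an ambiguity in a stated counting rule. Item 6 and Table 4 limit the row to 14 days, conflict with the lead-in to their own list, and leave open what the limit applies to. Under Reading A the row omits doses first withheld at Visit 6 or 7. Under Reading B it omits discontinuations from AEs starting on Days 15-59 or 74-179 at nominal visits, and a non-serious one may lack an AE record. The safety table can therefore read 0 while the disposition display shows a participant stopped for an AE with nothing behind the entry.

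The number or share of cases affected cannot be computed. The only rate given, about 20% discontinuation in Section 9.1, covers all causes. The conclusion rests on the scheduled visit days and on taking Table 2 as the reporting rule for SAEs; it does not depend on which reading was intended. This is a worthwhile, inexpensive correction on the primary objective, not a flaw that undermines the trial.

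**What to change.** 1. In Table 4, move the row for discontinuation due to an AE to the any-time column that already exists.
2. Reword item 6 as: any discontinuation of study vaccination or of the study due to an AE, at any time. This removes the conflict with the lead-in and states which kinds of discontinuation count.
3. In Section 8.4.1 and Table 2, require any AE that leads to discontinuation, serious or not, to be recorded with intensity and causality whenever it starts.

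The first two changes can be documented in the supplemental SAP before unblinding, as Section 9 provides. The third concerns data collection, so it belongs in the protocol text. No visit is added, because the criteria are already reviewed at Visits 6 and 7, and no rule for giving or withholding a dose changes.

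The cost is wording and, in an 18-person trial, at most a few extra AE records. The downside is that late events with a less certain link to vaccination enter this row; the recorded causality lets the reader separate them.
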